# 5.6.5 Follow-up

The following procedures and assessments will be performed on Days 10, 14 and 21 for Part 2:

- Measure vital signs (blood pressure, heart rate, respiratory rate, and oral body temperature)
- Collect PK blood samples (10 mL) after dosing as follows:
  - o Day 10: 216 hours after first dose on Day 1 (Part 2 only)
  - o Day 14: 312 hours after first dose on Day 1 (Part 2 only)
  - o Day 21: 480 hours after first dose on Day 1 (Part 2 only)
- Physical examination of skin at the sites of topical application for signs of irritation
- Symptom-directed brief physical examination at the investigator's discretion

- Record concomitant medications
- Monitor for AEs

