# **5.7.** Study Procedures

### 5.7.1 Pharmacokinetic Assessments

### 5.7.1.1 Pharmacokinetic Sample Collection

Pharmacokinetic blood samples (approximately 10 mL per sample) will be collected for determination of avobenzone, oxybenzone, octocrylene, ecamsule, homosalate, octisalate and octinoxate plasma concentrations (where applicable to the different sunscreen formulations) at the following time points (the time limit for PK sample draws can be +/-5 minutes from the nominal time):

- Day 1: 0 and 0.5, 1, 1.5, 2, 3 (Part 2 only), 4, 6, 8, 9, 10, 12, and 14 hours after initial dose
- Day 2: 23, 28, 33 h
- Day 3: 47, 52, 57 h
- Day 4: 71, 73, 74, 76, 78, 81, 82, 84 and 86 h
- Day 5: 95 hours
- Day 6: 120 hours
- Day 7: 144 hours
- Day 10: 216 hours (Part 2 only)
- Day 14: 312 hours (Part 2 only)
- Day 21: 480 hours (Part 2 only)

NOTE: when a time point corresponds with sunscreen administration, the PK sample will be collected before sunscreen administration.

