### Across all study days (Primary Endpoint)

• Maximum concentration (observed peak drug concentration) (Cmax)

#### Days 1

- Maximum concentration (observed peak drug concentration) (Cmax)
- Time at which  $C_{max}$  occurs  $(T_{max})$

• AUC from time 0 to the sampling time corresponding to the last quantifiable concentration (Clast) (AUC0-t), calculated by the mixed linear logarithmic trapezoidal method

### Days 2 and 3

- Residual drug concentration (predose level) (Ctrough)
- 3 h post dose concentration

### Day 4

- Elimination rate constant (Kel), obtained by linear regression of the log-linear terminal phase of the concentration-time profile using at least 3 data points, excluding Cmax, otherwise Kel will not be determined. The acceptability criteria for determination of Kel will be a coefficient of regression more than or equal to 0.98.
   When Kel will not be determined, AUC0-inf and t1/2 will not be reported.
- Terminal half-life  $(t_{1/2})$ , calculated using the equation  $\ln 2/k$  after the last study drug application (on Day 4)
- Accumulation ratios, calculated using the following formula:

$$R_1 = AUC_{0-23} Day 4 / AUC_{0-23} Day 1$$

• AUC from time 0 extrapolated to infinity (AUC0-inf), calculated by the mixed linear-logarithmic trapezoidal method as:

$$AUC_{0\text{-inf}} = AUC_{0\text{-t}} + C_{last} / K_{el}$$

When the extrapolation represents more than 20%,  $AUC_{0-inf}$  and  $t_{1/2}$  will not be reported.

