All data will be presented in data listings. Data from subjects excluded from an analysis population will be presented in the data listings but not included in the calculation of summary statistics. The number of subjects who enroll in the study and the number and percentage of subjects who complete each assessment will be presented. The frequency and percentage of subjects who withdraw or discontinue from the study and the reason for withdrawal or discontinuation will be summarized. Continuous demographic and baseline characteristic variables (age, height, weight, body mass index) will be summarized overall and by treatment using descriptive statistics (number of subjects, mean, standard deviation [SD], median, interquartile range [IQR], and minimum and maximum). The number and percentage of subjects in each class of categorical demographic and baseline characteristic variables will also be summarized.

5 Pharmacokinetic (PK) Analyses and Primary/Secondary Outcomes

The PK sampling schedule for this study is summarized in Appendix A. The following PK parameters will be determined for each subject in Part 1 and Part 2:

Across all study days

- Maximum concentration (observed peak drug concentration) (C_{\max})

Day 1

- Maximum concentration (observed peak drug concentration) (C_{\max})
- Time at which C_{\max} occurs (T_{\max})
- AUC from time 0 to the 23 hour time point (C_{last}) (AUC_{0-23})

Days 2 and 3

- Residual drug concentration (predose level) (C_{trough})
- Concentration 3 hours after the last dose of the day

Day 4

- Maximum concentration (observed peak drug concentration) (C_{\max})
- Time at which C_{\max} occurs (T_{\max})
- Elimination rate constant (K_{el}) and terminal half-life ($t_{1/2}$); calculated after final dose using all the available data up to last study sample (144 hours for Part 1; 432 hours for Part 2)
- AUC from time 71 to the 95 hour time point (AUC_{73-95})
- AUC from time 0 extrapolated to infinity ($AUC_{0-\text{inf}}$) and/or last observed time point

Day 5, 6, 7, 10 (Part 2 only), 14 (Part 2 only) and 21 (Part 2 only)

- Residual drug concentration (C_{trough})

The primary and secondary outcomes of this study are as follows:

Primary Outcome:

1. Maximum* Avobenzone concentration (C_{\max})

Secondary Outcomes:

1. Maximum* Oxybenzone concentration (C_{\max})
2. Maximum* Octocrylene concentration (C_{\max})
3. Maximum* Ecamsule concentration (C_{\max})
4. Maximum* Homosalate concentration (C_{\max})

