5. Maximum* Octisalate concentration (C_{\max})

6. Maximum* Octinoxate concentration (C_{\max}) (Part 2 Only)

* observed maximum;

Note that C_{\max} could occur on any of the days of the study. PK parameters C_{\max} , C_{last} , C_{trough} , T_{\max} , AUC_{0-t} , K_{el} , $t_{1/2}$ and $AUC_{0-\text{inf}}$, will be summarized using descriptive statistics (number of subjects, mean, standard deviation [SD], coefficient of variation [CV], median, minimum, and maximum) for the days above for avobenzone, oxybenzone, octocrylene, ecamsule, homosalate, octisalate and/or octinoxate (depending on whether the specific sunscreen formulation contains each of the active ingredients; see Attachment B) in Part 1 and 2. The PK parameters will be analyzed using non-compartmental methods based on actual sampling times. Mean and individual concentration-time profiles will be presented in graphs.

6 Safety Analyses

All AEs will be coded using the latest version of the Medical Dictionary for Regulatory Activities (MedDRA). The incidence of treatment-emergent adverse events (TEAEs), organized by system organ class and frequency, will be summarized by seriousness, severity, relationship to treatment, and by treatment at onset of the TEAE. A detailed listing of serious AEs and TEAEs leading to withdrawal will also be provided.

Clinical laboratory results (hematology, serum chemistry, and urinalysis) will be summarized using descriptive statistics (number of subjects, mean, SD, minimum, median, and maximum). Clinical laboratory results will be classified as normal or abnormal, according to the reference ranges of the individual parameter. The number and percentage of subjects with abnormal laboratory results will be provided. No statistical testing will be performed on clinical laboratory data.

Vital sign measurements (blood pressure, heart rate, respiratory rate, and oral body temperature), safety 12-lead ECG results, and changes from Baseline for these parameters will be summarized by treatment and time point using descriptive statistics (number of subjects, mean, SD, minimum, median, and maximum). Physical examination findings will be presented in a data listing, and abnormal physical examination findings will be recorded as AEs.

All concomitant medication usage and medications that changed in daily dose, frequency, or both since the subject provided informed consent will be summarized for each subject.

7 Missing Data

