Attachment A. Pharmacokinetic Sample Collection Schedule

Pharmacokinetic blood samples (approximately 10 mL per sample) will be collected for determination of avobenzone, oxybenzone, octocrylene, ecamsule, homosalate, octisalate and octinoxate plasma concentrations (where applicable to the different sunscreen formulations), at the following time points (the time limit for PK sample draws can be +/- 5 minutes from the nominal time):

- Day 1: 0 and 0.5, 1, 1.5, 2, 3 (Part 2 only), 4, 6, 8, 9, 10, 12, and 14 hours after initial dose
- Day 2: 23, 28, 33 h
- Day 3: 47, 52, 57 h
- Day 4: 71, 73, 74, 76, 78, 81, 82, 84 and 86 h
- Day 5: 95 hours
- Day 6: 120 hours
- Day 7: 144 hours
- Day 10: 216 hours (Part 2 only)
- Day 14: 312 hours (Part 2 only)
- Day 21: 480 hours (Part 2 only)

NOTE: when a time point corresponds with sunscreen administration, the PK sample will be collected before sunscreen administration.

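### Protocol 5.7.1.4 withholds t1/2 but not Kel when AUC extrapolation exceeds 20%, so t1/2 would be reported selectively by its own size; separately, SAP section 5 gives 432 h for a last Part 2 sample scheduled at 480 h

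*Protocol*

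**What the plan says.** Protocol 5.7.1.4 (Day 4) estimates Kel from the log-linear terminal phase with at least 3 points, excluding Cmax. The acceptance criterion "will be a coefficient of regression more than or equal to 0.98". If Kel is not determined, neither AUC0-inf nor t1/2 is reported. Half-life is ln2/k "after the last study drug application (on Day 4"). A second clause, opening "When the extrapolation represents more than 20" per cent, also withholds AUC0-inf and t1/2; it does not name Kel.

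SAP section 5 lists Kel and t1/2 together, "calculated after final dose using all the available data up to last study sample (144 hours for Part 1; 432 hours for Part 2"). It repeats neither the 20% clause nor the 0.98 criterion. Its parameter list, which includes both Kel and t1/2, "will be summarized using descriptive statistics (number of subjects, mean, standard deviation [SD], coefficient of variation [CV], median, minimum, and maximum").

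The Part 2 schedule ends later than 432 h. SAP Attachment A has "Day 21: 480 hours (Part 2 only"), and Protocol 5.6.5 fixes the clock: "Day 21: 480 hours after first dose on Day 1 (Part 2 only"). For Part 1 the last sample is "Day 7: 144 hours" (Protocol 5.7.1.1).

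**The concern.** The extrapolated share measures how far AUC0-inf can be trusted. The slope already has its own criteria, and t1/2 is a one-to-one function of that slope. Withholding t1/2 on the AUC criterion therefore reports a slope and suppresses the same information on another scale. The suppression also depends on the value suppressed: with a fixed last quantifiable time, a longer half-life leaves a larger share to extrapolate. Nothing is imputed (Protocol 5.9.9, SAP section 7), so the t1/2 row would describe a selected subset, in arms of only 6 subjects in Part 1. The same lotion is used in arms B and E, whose sampling ends at 144 h and 480 h, so the two summaries would be cut at different points.

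The 432 h figure matters because no sample falls between 312 h and 480 h. Read as a cut-off, it removes the whole Day 21 sample from the Part 2 terminal slope.

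**Working it through.** **1. The SAP's own figures.** Nominal hour = (Day − 1) × 24 from the first dose.
- Part 1, Day 7: 6 × 24 = 144 h. This reproduces.
- Part 2, Day 21: 20 × 24 = 480 h. The SAP's 432 h does not reproduce: 432/24 + 1 = Day 19, which is not a visit.
- Other origins do not explain it. From the first Day 4 application, 480 − 72 = 408 h; from the last, 480 − 78 = 402 h. Only the first Day 3 application gives 480 − 48 = 432 h, and that is not the final dose.

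**2. Half-life at which the share reaches 20%, all samples quantifiable.** Share = (Clast/Kel) / (AUC0-t + Clast/Kel). The last application is at 72 + 6 = 78 h. For simple exponential decline from then to the last sample T, the share is exp(−k(T − 78)). Setting this to 0.20 gives t1/2 = ln2 × (T − 78)/ln5.
- Part 1: 0.6931 × 66/1.6094 = 28.4 h.
- Part 2: 0.6931 × 402/1.6094 = 173.1 h.

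A one-compartment superposition on the scheduled applications and samples (linear-log trapezoid, assumed absorption half-life 1-8 h) gives:

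| AUC starts at | Part 1 limit | Part 2 limit |
|---|---|---|
| 0 h (Day 1) | 36.6-41.9 h | 180.6-185.3 h |
| 71 h (Day 4 predose) | 27.5-30.3 h | 173.4-175.3 h |
| 78 h (last application) | 25.7-28.3 h | 171.4-173.0 h |

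The Protocol lists AUC0-inf under Day 4 as starting at time 0, without saying which time 0. That choice alone moves the Part 1 limit by about 10 h.

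**3. Effect on the Part 1 mean t1/2.** Assume lognormal half-lives with median m, σ = √ln(1 + CV²), limit 40 h, and z = ln(40/m)/σ. Fall in mean = 1 − Φ(z − σ)/Φ(z). For m = 30 h and CV 50%: σ = 0.472, z = 0.609, and the fall is 1 − 0.554/0.729 = 24%.

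| Median t1/2 | CV 20% | CV 50% |
|---|---|---|
| 10 h | 0.0% | 0.5% |
| 20 h | 0.0% | 9.6% |
| 30 h | 3.4% | 24% |
| 40 h | 15.7% | 36% |

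**4. Share of this that the retained 0.98 rule causes anyway.** In simulation (Part 1 samples at 81-144 h, residual CV 10-20%, coefficient read as r-squared), the 0.98 rule alone lowers the mean by 2-4% at t1/2 CV 20%. At CV 50% it lowers it by 12-18% (median 30 h) and 15-19% (40 h). Dropping t1/2 from the 20% clause therefore recovers a net 2-3 points (CV 20%) to 13-15 points (CV 50%) at 30 h, and 13 to 22-24 points at 40 h. If the coefficient is r, the CV 50% gains are 14-17 and 23-26 points.

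**5. Adding a quantification limit (LOQ).** Protocol 5.7.1.4 ends AUC0-t at the last quantifiable concentration, not at a fixed time. The documents give no LOQ, so the peak/LOQ ratio is assumed (absorption half-life 2 h).
- Part 1, peak 10 × LOQ, AUC from 71 h: share 28% at t1/2 10 h, 9% at 20 h, 20% at 30 h. A short half-life can be the one removed. With AUC from Day 1, the share is 12% or less at these half-lives.
- Part 2, peak 4 × LOQ: share about 22-30% at t1/2 40 h and 36-44% at 60 h. The clause then acts in Part 2 as well.

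**6. 432 h read as a cut-off.** The SE of the slope is proportional to 1/√Sxx.
- All points from 81 h: Sxx = 157,298 to 480 h and 50,520 to 312 h; √(157,298/50,520) = 1.76.
- Last 3 points: Sxx = 35,712 (216, 312, 480 h) and 14,208 (144, 216, 312 h); √(35,712/14,208) = 1.59.
- These apply only if the 480 h sample is quantifiable. At t1/2 60 h the 480 h level is about 1% of peak; with peak 50 × LOQ the last quantifiable sample is already 312 h, and nothing is lost.

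**The case against.** A reader might infer that the clause biases the Part 1 half-life low, is inert in Part 2, and that the Day 21 sample will be lost. The documents support none of these flatly.

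- **Which text governs is unsettled.** The SAP carries no 20% clause and calls for all available data. If the SAP governs, there is no selection from this source. This stands: the effect is conditional on the Protocol clause being applied, and the two texts need reconciling.
- **No half-life or LOQ is given.** Below a 20 h median the effect is small, and a high LOQ can change which half-lives are removed and bring Part 2 in. This stands for size and direction. It does not remove the defect, which is that reporting of t1/2 depends on t1/2.
- **432 h is probably a slip.** The operative words are the last study sample, and Attachment A has 480 h. This is fair; use as a cut-off is only a possibility. The figure is still wrong and should be corrected.
- **Withholding is a reasonable reliability screen.** Follow-up of 66 h is only about 2.3 half-lives at the 28.4 h limit. This has some force, but it is an argument for screening the slope. The clause leaves Kel, which is no more reliable, in the summary.

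**Conclusion.** Two textual defects hold. The 20% clause withholds t1/2 but not Kel, and 432 h contradicts the 480 h schedule in both documents. If the clause is applied, t1/2 is selected by its own size and its summary covers different subjects from the Kel summary. Where levels stay quantifiable to the last sample, the long half-lives go and arms B and E are truncated differently. The fall in the Part 1 mean then ranges from under 1% to 36% across assumed medians of 10-40 h, with a 40 h limit and t1/2 CV of 20-50%; part of it would remain under the 0.98 rule. Where peaks are only a few times the LOQ, the clause can also remove short half-lives (AUC from Day 4) and can act in Part 2. The 432 h figure costs up to a 1.76-fold (all points) or 1.59-fold (last 3) rise in the SE of Kel if taken literally with a quantifiable Day 21 sample, and nothing otherwise.

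The point is minor. Half-life is neither a primary nor a secondary outcome, Cmax is unaffected, all data are listed, and a withheld t1/2 equals ln2/Kel. Confidence is high on the text and conditional on the size.

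**What to change.** - **Protocol 5.7.1.4:** apply the 20% limit to AUC0-inf only. Report t1/2 whenever Kel meets its criteria, flagged with the extrapolated fraction. Give the number not estimable per arm and ingredient.
- **SAP section 5:** change 432 to 480 hours. State the same Kel rule as the Protocol (terminal phase, minimum of 3 points, Cmax excluded, 0.98) and say whether the coefficient is r or r-squared. State the start time of the Day 4 AUC used for the 20% limit.

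The cost is wording only, with no change to subjects, samples or procedures. The downside is precision: the long Part 1 half-lives that are kept are less well estimated. With the seven samples over 81-144 h (Sxx = 3,489), the CV of Kel is roughly residual CV/(Kel × √Sxx). That is about 7% at t1/2 30 h and 15% at 60 h for residual CV 10%, and about 15% and 29% for residual CV 20%. The flag and the count make this visible, along with the selection that the 0.98 rule leaves.

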### Days 5, 6, 7, 10 (Part 2 only), 14 (Part 2 only) and 21 (Part 2 only)

• Residual drug concentration (Ctrough)

### **5.7.2** Safety Assessments

Safety will be evaluated in terms of AEs, vital sign measurements (blood pressure, heart rate, respiratory rate, and oral body temperature), and physical examination findings.

### 5.7.2.1 Adverse Events

#### 5.7.2.1.1 Adverse Event Definitions

An AE is defined as any untoward and/or unintended sign, including an abnormal clinical laboratory finding, symptom, or disease temporally associated with the use of a study drug, whether or not considered related to the study drug. Events or conditions that

increase in frequency or severity during or as a consequence of use of a drug in human clinical trials will also be considered AEs.

A treatment-emergent adverse event (TEAE) is defined as an AE that begins after study drug administration.

An unexpected AE is any AE having a specificity or severity not consistent with the current investigator's brochure for the study drug(s).

An SAE is defined as any AE occurring at any dose that meets the following criteria:

- Results in death,
- Is life threatening,
- Requires hospitalization or prolongation of existing hospitalization,
- Results in persistent or significant disability or incapacity,
- Is a congenital anomaly/birth defect, or
- Is an important medical event that may not meet the previous criteria but, based upon appropriate medical judgment, jeopardizes the subject or requires medical or surgical intervention to prevent one of the outcomes listed previously.

# 5.7.2.1.2 Adverse Event Reporting

The recording of AEs will begin after the subject signs the informed consent form and will continue until discharge (or early termination). All AEs, whether serious or nonserious and whether or not related to the study drug, must be recorded in the eCRF. Study subjects will be instructed to warn study staff if he or she has any unexpected symptoms. In addition, all subjects will receive a reminder telephone call approximately 24 hours before Check-in.

Any SAE (whether expected or unexpected) must be entered into the eCRF system and reported by facsimile to the medical monitor or designee using the SAE Reporting Form within 24 hours of the investigator or study clinic staff becoming aware of the event. It is the responsibility of the investigator to report all SAEs to the medical monitor, to provide the most complete report possible, and to assess each SAE for its relationship to the study drug. The investigator is responsible for obtaining follow-up information on all SAEs and submitting follow-up SAE data. Any unexpected SAEs must be reported promptly to the investigator's IRB as per the IRB's requirements.

In the event of a fatal or life-threatening SAE, the sponsor will notify the appropriate FDA authorities by telephone or facsimile within 7 calendar days of receipt of the report. The sponsor will follow all 7-day alert reports with a written report within 10 working days of receipt of the case. Serious AE cases that concern nonfatal, nonlife-threatening

events that are unexpected and at least possibly related to the study drug will be submitted in writing to the FDA within 10 working days of receipt.

Furthermore, any AEs that are not expected, occur at a higher frequency, or would require modification of the study protocol and/or informed consent must be reported to the FDA within 10 working days.

Adverse events that are assessed by the investigator as possibly or probably related to the study drug will be followed until they resolve or stabilize. All SAEs will be followed until resolution.

### 5.7.2.1.3 Assessment of Severity

The investigator will assess the severity of each AE using the following scale:

- Mild: The subject is aware of the AE but is still able to perform all activities; minimal or no medical intervention or therapy is required.
- Moderate: The subject has to discontinue some activities due to the AE; minimal or no medical intervention or therapy is required.
- Severe: The subject is incapacitated by the AE and is unable to perform normal activities; significant medical intervention or therapy is required and hospitalization is possible.

# 5.7.2.1.4 Assessment of Causality

The investigator will assess the causal relationship/relatedness of each AE to the study drug using the following scale:

- Not Related: Onset of the AE has no reasonable temporal relationship to administration of the study drug, a causal relationship to administration of the study drug is biologically implausible, or the event is attributed to an alternative etiology.
- Unlikely Related: Onset of the AE has a reasonable temporal relationship to study drug administration and although a causal relationship is unlikely, it is biologically plausible.
- Possibly Related: Onset of the AE has a strong temporal relationship to administration of the study drug, cannot be explained by the subject's clinical state or other factors, and a causal relationship is biologically plausible.
- Probably Related: Onset of the AE shows a distinct temporal relationship to administration of the study drug that cannot be explained by the subject's clinical state or other factors, the AE is a known reaction to the product or chemical group, or can be predicted by the product's pharmacology.

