#### 5.1.5 Risk/Benefit

Subjects will be informed that participation in a human PK study like the present one cannot be of benefit to healthy volunteers. Nevertheless, the information from the physical examination, vital sign measurements, and ECG results may be shared with the subject's personal physician if this is the subject's choice. Subjects will be informed that

it is also their choice to inform their personal physician that they are participating in this research study.

Subjects will be informed that their contribution to the study is of major importance to agencies like the U.S. FDA for helping this agency better evaluate the effects of human systemic absorption of sunscreen ingredients. However, since this is a study involving healthy volunteers, subjects will be informed that they have the alternative not to participate.

Subjects will be informed that they may be exposed to risks associated with the pharmacological properties of the study drugs and the study procedures.

The study sunscreen products will not be administered to anyone who is pregnant. All women must take a pregnancy test before receiving any study drug in this study. All men and all women of childbearing potential enrolled in this study will be informed that they must use 2 highly effective birth control methods (as determined by the investigator or designee; one of the methods must be a barrier technique) during the study and for at least 1 month after the last application of study drug. Subjects will be informed that they must notify the investigator if they or their female partners become pregnant during the course of the study.

Subjects will be informed that insertion of an IV catheter may be required for blood sample collection on Days 1 and 4 and, during insertion of the catheter, soreness, bruising, or infection at the insertion site are possible but unlikely. Subjects will also be informed that dizziness and lightheadedness may occur during direct venipuncture, insertion of the IV catheter, or during blood collection.

Subjects will be informed that tape stripping applied to the skin may cause mild pain or irritation and skin rash at the area of tape stripping after the procedure.

Subjects will be informed that they may eat only meals and snacks that are provided during periods of their stay in the study clinic, and that they must consume all of each meal that is served at a reasonable pace (within 25 minutes).

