### 5.5. Criteria for Subject Withdrawal

Subjects may withdraw from the study at any time at their own request, or they may be withdrawn by the investigator without the approval of the subject based on the investigator's clinical judgment. A subject is not required to provide a written request to withdraw from the study; however, a written request is required if a subject withdraws consent for his or her personal data to be used for study-related purposes.

A subject may be discontinued for any of the following reasons:

- AE: The subject has experienced an AE that, in the opinion of the investigator, requires early termination. The appropriate electronic case report form (eCRF) must be completed for each AE. If a subject is discontinued from the study due to an AE, the investigator is required to follow up with the subject until the event resolves or becomes stable. If a subject dies during the study, the cause of death must be reported as a serious AE (SAE), with an outcome of death noted in the eCRF.
- Protocol Violation: The subject failed to meet protocol entry criteria or did not adhere to protocol requirements, and continued participation poses an unnecessary risk to the subject's health.
- Withdrawal by Subject: The subject (or other responsible individual [e.g., caregiver]) wishes to withdraw from the study in the absence of a medical need.
  - NOTE: Withdrawal due to an AE should not be recorded in the "voluntary withdrawal" category.
- Study Terminated by Sponsor: The sponsor, IRB, FDA, or other regulatory agency terminates the study.
- Pregnancy: The subject is found to be pregnant.
  - NOTE: If the subject is found to be pregnant, the subject must be withdrawn immediately. The pregnancy will be followed up to term, and the outcome, including any premature termination will be recorded. All live births must be followed for a minimum of 30 days or until the first well baby visit.
- Other.

NOTE: This category records withdrawals caused by an accidental or a medical emergency, unblinding, and other rare cases. The specific reason should be recorded in the comment space of the eCRF.

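### Possibly Related carries the same no-other-explanation test as Probably Related, so a well-timed, plausible AE with an unresolved competing cause has no proper grade and may be under-graded

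*Protocol*

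**What the plan says.** Protocol section 5.7.2.1.4 defines four grades.

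- **Not Related** applies when timing is not reasonable, when a causal link is implausible, "or the event is attributed to an alternative etiology".
- **Unlikely Related** needs reasonable timing and the judgement that "although a causal relationship is unlikely, it is biologically plausible".
- **Possibly Related** needs biological plausibility and an onset that "has a strong temporal relationship to administration of the study drug, cannot be explained by the subject's clinical state or other factors".
- **Probably Related** needs a distinct temporal relationship that "cannot be explained by the subject's clinical state or other factors, the AE is a known reaction to the product or chemical group", or a reaction predictable from the product's pharmacology.

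Two rules in Protocol section 5.7.2.1.2 use the grade. On follow-up: "Adverse events that are assessed by the investigator as possibly or probably related to the study drug will be followed until they resolve or stabilize". On reporting, SAEs that are neither fatal nor life-threatening go to the FDA in writing if they are unexpected and at least possibly related. The next paragraph sends AEs that are not expected to the FDA with no causality condition.

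Protocol section 5.9.7.1 and SAP section 6 both summarise AEs by relationship to treatment. Neither says which grades count as related.

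**The concern.** A four-step causality scale normally uses its middle grade for events that could be due to the drug but could also be due to something else. Here that grade is closed to such events, because the test that should separate Probably from Possibly appears in both. An investigator facing a real ambiguity must choose between grades that do not fit, and the two lower grades are the natural default.

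The grade carries weight in this trial. It is open-label (Protocol section 5.8.5) and has no reference product (Protocol synopsis), so there is no untreated AE rate to compare with. The investigator's causality grade is the main evidence on attribution. It also controls part of the follow-up and one FDA-reporting threshold.

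**Working it through.** No figure in the plan can be reproduced here. The check sets the definitions beside one another and then beside each rule that uses the grade.

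**Step 1. Grade a test event.** Take an event with strong timing and biological plausibility, a competing cause that has not been settled, and no judgement that drug causation is unlikely.

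- Possibly Related: fails. Its three conditions are joined by *and*, and the event can be explained by another factor.
- Probably Related, criteria read as cumulative: fails on the same exclusion.
- Probably Related, criteria read as alternatives: met if the event is a known or predictable reaction. The event then qualifies as Probably while failing Possibly, and the scale is out of order.
- Unlikely Related: fails, because causation is not judged unlikely.
- Not Related: fails, because the event has not been attributed to the other cause.

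On the cumulative reading no grade fits. On the alternative reading the order of the grades breaks.

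**Step 2. Can this trial produce such events?** Protocol section 5.1.5 says dizziness and lightheadedness may occur with venipuncture, catheter insertion or blood collection. The schedule in section 5.7.1.1 gives, for Days 1 to 4:

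- Part 1: 12 + 3 + 3 + 9 = 27 draws per subject
- Part 2: 13 + 3 + 3 + 9 = 28 draws per subject
- All planned subjects: 24 × 27 + 48 × 28 = 648 + 1,344 = 1,992 draws

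Apart from the pre-dose sample on Day 1, these draws fall among or soon after applications, so an event can be close in time to both the drug and a draw. The total counts opportunities for ambiguity. It does not count events.

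**Step 3. What does a lower grade change?**

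- *Follow-up.* Other rules apply whatever the grade. For SAEs: "All SAEs will be followed until resolution". For an AE that leads to discontinuation: "the investigator is required to follow up with the subject until the event resolves or becomes stable" (Protocol section 5.5). Section 9.3.2 keeps all dosed subjects under safety follow-up at all follow-up visits. What remains exposed is a nonserious AE that does not cause discontinuation and is still unresolved at the last scheduled visit. That visit is Day 7 in Part 1 and Day 21 in Part 2.
- *FDA reporting.* An unexpected SAE that is neither fatal nor life-threatening, if graded below Possibly, misses the written-report threshold. Read literally, the next paragraph of section 5.7.2.1.2 would still capture it. The two rules then disagree on whether causality matters.
- *Tables.* The event moves to a lower row of the by-relationship summary. It stays in the AE totals and in the listings (Protocol section 5.9.3, SAP section 4).

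**The case against.** The strongest reply is that the safeguards that do not depend on the grade cover most of what matters. All AEs are recorded. SAEs go to the medical monitor within 24 hours and unexpected SAEs to the IRB. Part 2 subjects have skin examination and AE monitoring on Days 10, 14 and 21. Safety is descriptive, the products are OTC, and no stated conclusion rests on a count of related AEs. A competing cause alone does not meet Not Related, so a fall to the lower grades is an inference about how investigators behave. All of this stands, and it limits the consequence. It does not supply the missing grade.

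A reader might infer three stronger things that the documents do not support.

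- *That ambiguous events drop out of follow-up and out of a related-AE table.* Step 3 shows that the follow-up loss is narrow. Neither document defines a pooled related category for events to drop out of.
- *That lower-back rash after tape stripping is the leading case.* The protocol does warn that "tape stripping applied to the skin may cause mild pain or irritation and skin rash", and the torso is treated skin. But the last application is nominally at 72 + 6 = 78 h. Stripping is on Days 7 and 14. No clock time is given for it, so I take the PK samples on those days, at 144 h and 312 h, as a guide. The gaps are 144 − 78 = 66 h and 312 − 78 = 234 h. The requirement for strong timing may exclude such a rash before the exclusion is reached.
- *That 48 × 2 = 96 stripping sessions measures the problem.* It counts procedures well after dosing and says nothing about misgraded events.

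**Conclusion.** The defect is in the stated definitions: the same exclusion sits in both upper grades, and a well-timed, plausible event with an unresolved competing cause has no proper home. Under-grading is likely but not certain.

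The consequence has three limited parts: follow-up of some nonserious AEs after scheduled visits end, one written FDA-report threshold that conflicts with the paragraph after it, and placement within the by-relationship summaries. The number of events cannot be estimated from the documents. The primary endpoint, Cmax, does not depend on any of this.

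The conclusion assumes that investigators apply the definitions as written and that no separate grading guide alters them. The dizziness example also assumes that the investigator finds a drug cause biologically plausible, which the documents do not settle.

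**What to change.** 1. In Protocol section 5.7.2.1.4, remove the exclusion from Possibly Related. Keep its timing and plausibility conditions, and state that the event may also be explained by the subject's clinical state, a study procedure or another factor.
2. Keep the exclusion for Probably Related only, and say whether its criteria must all be met or are alternatives.
3. In section 5.7.2.1.2, reconcile the at-least-possibly-related threshold with the paragraph that reports unexpected AEs whatever their cause, and confirm that the follow-up rule works as intended with the revised grades.
4. In SAP section 6, state which grades count as related if any pooled count will be reported.

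The cost is a sentence or two in each place and a matching line in the eCRF completion guide. The downside is that more AEs will be graded possibly related and followed until they resolve or stabilise. The Part 2 product that was to be chosen from Part 1 data is already named, so Part 1 grading may be complete. If so, the report should say which definition applied to each part, or the Part 1 events should be regraded.
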